**Specific Aim 1** will examine the effects of a 4-month, remotely delivered EFT intervention on delay discounting, medication adherence, diet, physical activity, body weight, and glycemic control in patients with poorly controlled T2D. All participants will receive access to a standard behavioral treatment (BT), including lifestyle coaching, dietary and activity education, and daily self-monitoring. Participants assigned to an EFT+BT group will also be asked to generate vivid, episodic events and be sent text-based prompts daily to engage in EFT in the natural environment with the assistance of a study website. Participants assigned to a BT alone group will not receive EFT, but will be asked to access the study website and answer questions about their experience with the same frequency as the EFT group in order to control for use of the technology, effort, attention, and experimenter contact. We will assess outcome measures both during and immediately after the intervention, as well as at a 6-month follow-up session (approximately 2 months following the end of the intervention). This will allow us to estimate both short- and long-term effects changes in behavior, weight, and glycemic control

**Specific Aim 2** will examine the acceptability of the remote EFT intervention. In order for an intervention to be effective in clinical settings, it should be easy to use and its helpfulness should be apparent. Thus, during the trial and follow-up, participants will rate all aspects of the interventions along several dimensions, including helpfulness and ease of use. High intervention ratings would suggest that EFT may be implemented with high treatment fidelity in clinical settings and is more likely to be disseminated among treatment providers and adopted by patients.

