**-Laboratory Assessment Sessions (Weeks 0, 8, 16, and 24)**

At assessment sessions, we will collect measures of blood HbA1c, blood pressure, height, and weight. Participants will also complete delay discounting tasks, food purchase tasks, and complete other study questionnaires (e.g., demographics).

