#### **Data analysis:**

We will use repeated measures ANOVA to examine changes in delay discounting, glycemic control, dietary intake, physical activity, medication adherence, BMI, and body composition (Specific Aim 1), as well as acceptability of the intervention (Specific Aim 2) in subjects who are randomly assigned to EFT and control conditions. Covariates will be included, as appropriate, including gender and socioeconomic status.

We will test for attrition bias by comparing participants who drop out versus those who complete the study. We will use intention to treat methods, and include all randomized subjects. We have a rigorous retention plan but expect up to 15% attrition. We will use maximum likelihood-based procedures to impute missing data. This approach is associated with more accurate parameter estimates than other approaches (e.g., last-observation carried forward), and is appropriate even when missing data are not missing at random

Statistical review was conducted by: **[name]** (name of statistician)  
**Fralin Biomedical Research Institute** (Department/Institution of statistician)

If no statistical review was done, explain why:

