**\*\*\*If this study is a retrospective record review only, you may skip to Section VII\*\*\***

31. Will subjects receive any compensation or gifts to participate?

Yes       No       N/A

- If yes, specify payment amount, how it will be prorated and how payment will be made: **Participants may receive up to \$300 for completion of all study procedures, as follows.**
  - **Assessment Session 1 (Week 0): \$20**
  - **Assessment Session 2 (Week 8): \$30**
  - **Assessment Session 3 (Week 16): \$35**
  - **Assessment Session 4 (Week 24 follow-up, post-intervention): \$40**
  - **Physical Activity and Diet Assessments 1-3 (Weeks 0, 8, and 16): \$20 per assessment week (\$60 total possible). These will occur outside the laboratory. At each assessment, participants will be asked to wear the Actigraph accelerometer to measure physical activity for a period of seven days. On three of those days, participants will also be asked to complete the ASA-24 dietary recall questionnaire online.**
  - **Brief Online Assessments (Weeks 3, 9, and 15). \$5 per assessment (\$15 total possible). Participants will be asked to complete brief online assessments (e.g., delay discounting, food purchasing) outside of the laboratory. EFT+BT participants will also be asked to complete an EFT event/cue-generation exercise.**
  - **Participants will also receive an additional bonus at Week 24 of \$100 for completing 90% or more of all assessment sessions and at-home assessments (Actigraph, brief online assessments, and diet recalls). The magnitude of this bonus was chosen in order to motivate attendance at the follow-up assessments for the majority of participants and thus minimize the occurrence of missing data, including from those participants who may have been less successful in the intervention or follow-up period.**

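### The plan says maximum likelihood handling of missing data holds even when data are not missing at random. With no dropout model it does not, and no sensitivity analysis is planned.

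*Combined protocol and SAP*

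**What the plan says.** Section III, item 24 (Data analysis) plans repeated measures ANOVA on an intention-to-treat basis with every randomized participant included. The investigators "expect up to 15% attrition". On missing values the plan says: "We will use maximum likelihood-based procedures to impute missing data". It gives two reasons for that choice: better parameter estimates than approaches such as last observation carried forward, and that the method "is appropriate even when missing data are not missing at random".

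The only attrition check is in the same item: "We will test for attrition bias by comparing participants who drop out versus those who complete the study". No selection, pattern-mixture, delta-adjusted, reference-based or tipping-point analysis appears anywhere in the document.

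Two other places bear on the point. Section V, item 31 sets a $100 completion bonus to limit missing data, "including from those participants who may have been less successful in the intervention or follow-up period". On differences between arms, Specific Aim 1 (item 18) has controls use the website "with the same frequency as the EFT group in order to control for use of the technology, effort, attention, and experimenter contact", but item 31 adds that "EFT+BT participants will also be asked to complete an EFT event/cue-generation exercise".

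**The concern.** The second reason given for the method attributes to it a property it does not have. Likelihood inference that ignores the dropout process is justified under MAR, which includes missing completely at random, with a correctly specified model. Under MNAR it is not justified in general.

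The sentence also has an effect on the rest of the plan. If the method really covered MNAR, no sensitivity analysis would be needed, and none is planned. The dropout-versus-completer comparison cannot take its place: it sees only recorded values, so it can neither rule out nor correct dependence on unrecorded ones.

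If dropout depends on unseen outcomes, and its rate or mechanism differs by arm, the arm contrast is biased. The direction depends on which arm loses more of its poor responders. As written, the plan gives no way to see how far a result depends on MAR.

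A smaller gap sits beside this one: the plan does not say how likelihood-based imputation is combined with repeated measures ANOVA.

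**Working it through.** **Planning figure.** Inputs from item 24 (Sample size justification): f = .25, alpha = .05, correlation .50, 95% power, N = 54. Two groups and m = 2 measurements are assumed.

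- Noncentrality = f² × N × m / (1 − rho) = 0.0625 × 54 × 2 / 0.5 = 13.5. With 1 and 52 degrees of freedom, power is 0.950, so N = 54 reproduces.
- In a 2 × 2 interaction, f = .25 means cell effects of ±0.25 SD, so the difference in change is 4 × 0.25 = 1.0 SD. This is the yardstick below.
- To finish with 54 at 15% loss: 54 / 0.85 = 63.5, so 64 randomized, or 32 per arm (1:1 assumed).

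**Strength of the attrition check.** 64 × 0.15 = 9.6, so about 10 dropouts against 54 completers. The standard error of a standardized difference is √(1/10 + 1/54) = 0.344. For a true difference of 0.5 SD the noncentrality is 0.5 / 0.344 = 1.45, and two-sided power on 62 degrees of freedom is 0.298. Power reaches 80% only at a difference of 0.98 SD. Even at full power it would test observed values only.

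**Bias under MNAR.** Simulation with 8,000 trials per scenario, 32 per arm, visits at Weeks 0, 8, 16 and 24 (item 22), correlation .5 between all visits and no true effect. The analysis is a maximum likelihood Week 24 contrast adjusted for baseline, using all observed visits. The chance of dropout rises with the unseen value, at a logit slope of 1 or 2 per SD. Dropout falls either all at Week 24 or over Weeks 8, 16 and 24. Entries are bias in SD (type I error) at slope 1, then slope 2. Negative favours EFT where lower is better.

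| Dropout EFT/BT | All at Week 24 | Spread over Weeks 8–24 |
|---|---|---|
| 15/15, same mechanism | −0.001 (4.9%), +0.002 (4.7%) | 0.000 (4.5%), +0.001 (4.3%) |
| 20/10 | −0.052 (5.8%), −0.078 (6.0%) | −0.036 (4.7%), −0.054 (5.3%) |
| 25/5 | −0.108 (6.7%), −0.162 (9.9%) | −0.072 (5.8%), −0.110 (6.7%) |
| 10/20 | +0.053 (5.4%), +0.082 (6.3%) | +0.034 (5.1%), +0.057 (5.1%) |
| 5/25 | +0.109 (6.9%), +0.161 (10.4%) | +0.070 (5.5%), +0.110 (7.1%) |
| 15/15, informative in EFT only | −0.085 (6.1%), −0.130 (7.9%) | −0.053 (5.2%), −0.084 (5.8%) |

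The Monte Carlo standard error near 5% is √(0.05 × 0.95 / 8000) = 0.24 percentage points. Type I errors of 4.7 to 5.3% are therefore not distinguishable from nominal.

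**Contrast with MAR.** When dropout depends on the recorded Week 16 value instead, absolute bias is at most 0.003 SD and type I error is 4.4 to 4.8%, at 15/15, 20/10 and 25/5. The method works under the assumption it needs and fails only when that assumption fails.

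**Within-arm change.** With the same mechanism and 15% loss at Week 24 in both arms, the arm contrast is unbiased because the errors cancel. A large-sample calculation still gives about 0.09 to 0.14 SD of false improvement in each arm. The hypotheses in item 19 include improvement within the EFT group, so this case is not harmless.

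**The case against.** The authors may have meant not missing *completely* at random, which would make the sentence nearly correct. The text does not say that, and if it is what was meant, the correction is one line.

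The plan does act on outcome-related dropout through its conduct. It has a retention plan, intention-to-treat inclusion, and a bonus aimed at participants doing less well. This deserves credit and should lower the loss. It does not make the validity statement true. Nor does the bonus wording establish MNAR, since dropout driven by poor values already recorded at Week 8 or 16 is MAR.

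The strongest objections go to size, and they stand:

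- Every scenario uses 15% average loss, which the plan gives as a ceiling. At 8% average loss with the same 2:1 split (5,000 trials), bias is 0.02 to 0.05 SD and type I error 4.2 to 5.2%.
- If all dropout comes at Week 24, a Week 16 contrast is unaffected. The plan names no primary time point.
- The figure near 10% needs a fivefold difference in dropout between arms, the steeper slope and all loss at the last visit. Nothing in the document predicts that combination.
- The simulated contrast is not the planned group-by-time ANOVA. It illustrates likelihood analysis under MNAR rather than measuring this plan's exact test.
- Contact is largely matched between arms. The extra cue task shows only that equal dropout cannot be assumed, not that it will differ.

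None of these rescues the sentence or supplies the missing analysis.

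**Conclusion.** The concern holds and should be fixed. The validity claim is wrong for a likelihood method without a dropout model, and the plan contains nothing that would show dependence on MAR.

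The likely damage is modest. At the 15% ceiling and under the assumed slopes and timing, the Week 24 contrast is biased by 0.04 to 0.08 SD for a 20/10 or 10/20 split, 0.07 to 0.16 SD for 25/5 or 5/25, and 0.05 to 0.13 SD if only EFT dropout is informative. Against the 1.0 SD planning difference that is 4 to 16%. Type I error runs from nominal to about 10% at the extreme. Bias is nil if rate and mechanism match between arms, or if dropout is MAR.

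These figures are illustrations, not predictions. The incorrect statement and the missing sensitivity analysis do not depend on them.

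**What to change.** 1. Replace the clause in item 24 with a statement that the likelihood-based analysis is valid if data are missing at random given the observed data and the model is correctly specified.
2. Name one primary method: a likelihood-based mixed model using all observed visits of all randomized participants. This also settles how the handling of missing data fits with the main analysis.
3. Pre-specify a delta-adjusted (tipping-point) analysis for HbA1c and delay discounting. Vary the departure from MAR separately in each arm, for example from 0 to 1 SD in steps of 0.25 SD, and report where the conclusion changes or that it does not. The contrast moves by p_EFT × delta_EFT − p_BT × delta_BT, where p is the proportion missing. At 15% missing per arm, a 1 SD departure in one arm moves it 0.15 × 1 = 0.15 SD; equal departures in both arms cancel. A result that survives the whole grid is worth reporting as such.
4. Keep the dropout-versus-completer comparison as description, and state that a non-significant result is not evidence of no bias.

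The cost is revised analysis wording and a few extra model runs. No new data or participants are needed, and N = 54 is unchanged.

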#### **SECTION IV: RISKS AND BENEFITS**

25. Summarize the possible risks to subjects and how they have been minimized in the study design. Include risk of psychosocial harm (e.g., emotional distress, embarrassment, breach of confidentiality), economic harm (e.g., loss of employment or insurability, loss of professional standing or reputation, loss of standing within the community) and legal jeopardy (e.g., disclosure of illegal activity or negligence), as well as known side effects of study medication, if applicable, and risk of pain and physical injury. Define the level of risk (minimal risk, risk but with potential benefit to patient, risk but no benefit to patient). Describe any procedures that will be used to prevent or minimize risks or discomforts. Note: Most studies create at least a small risk of breach of confidentiality or privacy.

**Overall, the risks of study participation are minimal. Participants will be informed of the risks associated with the study.**

**In subjects who are enrolled with an A1c between ~8% and 9.9%, an A1c over 10% will trigger a notification of their physician or appropriate medical referral. In**

**subjects who are enrolled with an A1c  $\geq 10\%$ , any 1 percentage point increase over baseline will trigger a notification of their physician or appropriate medical referral.**

**Participants will be free to withdraw from the study at any time, and their refusal to continue will not affect other medical care provided at any healthcare facility.**

**Participants might feel uncomfortable disclosing some personal information such as medical history. Participants might experience adverse effects associated with changes in diet, including feeling hungry, fatigue, or headache.**

**Participants may, if they are on sulfonylurea or glinide medications, experience symptoms associated with hypoglycemia. Given that insulin use is an exclusion for this study, this is likely to be an uncommon and mild clinical issue. Participants will be instructed to discuss the possibility of hypoglycemia with their treating physician and the case managers will educate participants about hypoglycemic reactions and advise those on hypoglycemic medications to carry an additional source of ready sugar.**

**Participants may experience possible discomfort from blood glucose testing (e.g., momentary pain, skin irritation).**

**To protect confidentiality, we will use only ID numbers and keep all data in locked offices and/or password-protected databases. Any data sharing between sites will involve de-identified data only and files will be encrypted or password protected. These screening, monitoring, and confidentiality procedures have been in effect for more than 15 years and for more than 2,000 subjects across the various protocols employed by our group.**

26. Describe all costs, if any, subjects may incur as a result of being in this study.

**Costs to the patient include required to travel to the FBRI or CRC sites where participants will complete assessment sessions. However, the compensation provided for participation should adequately cover these costs, including a bonus for completing this 6-month study. The intervention itself has been designed to be remotely delivered and, thus, pose minimal costs.**

27. Describe how subjects will be compensated for injury incurred as a result of being in the study.

**Subjects will not be compensated if they are in some way injured because of participation in this study.**

28. Is any deception used in the study or any aspect of the study kept secret from the subjects, such as the full purpose of the study?

Yes       No

• If yes, describe the deception involved and the debriefing procedures:

29. Describe any direct benefit to individual subjects, to the group of individuals with the disease process you are researching, and/or to society based on scientific knowledge gained. Explain how the potential benefits offered by this research outweigh the risks. (Please note: payments, gifts, or other free services given as a token for participation are not benefits, but instead are classified as compensation.)

**Participants may benefit from possible weight loss and improved glycemic control.**

## **SECTION V: RECRUITMENT**

30. Number of Subjects/Enrollment Goal. The enrollment goal must match the number of subjects needed to meet the primary outcome. If this is a retrospective record review, this figure is the number of records that will be used for analysis. Prior IRB approval must be given to exceed the enrollment goal.

Locally: **Up to 150 enrolled, (N = 54 target completion goal, plus additional if necessary to account for possible dropout, screen failure, etc.)** At all Sites: **up to 150**

**\*\*\*If this study is a retrospective record review only, you may skip to Section VII\*\*\***

31. Will subjects receive any compensation or gifts to participate?

Yes       No       N/A

- If yes, specify payment amount, how it will be prorated and how payment will be made: **Participants may receive up to \$300 for completion of all study procedures, as follows.**
  - **Assessment Session 1 (Week 0): \$20**
  - **Assessment Session 2 (Week 8): \$30**
  - **Assessment Session 3 (Week 16): \$35**
  - **Assessment Session 4 (Week 24 follow-up, post-intervention): \$40**
  - **Physical Activity and Diet Assessments 1-3 (Weeks 0, 8, and 16): \$20 per assessment week (\$60 total possible). These will occur outside the laboratory. At each assessment, participants will be asked to wear the Actigraph accelerometer to measure physical activity for a period of seven days. On three of those days, participants will also be asked to complete the ASA-24 dietary recall questionnaire online.**
  - **Brief Online Assessments (Weeks 3, 9, and 15). \$5 per assessment (\$15 total possible). Participants will be asked to complete brief online assessments (e.g., delay discounting, food purchasing) outside of the laboratory. EFT+BT participants will also be asked to complete an EFT event/cue-generation exercise.**
  - **Participants will also receive an additional bonus at Week 24 of \$100 for completing 90% or more of all assessment sessions and at-home assessments (Actigraph, brief online assessments, and diet recalls). The magnitude of this bonus was chosen in order to motivate attendance at the follow-up assessments for the majority of participants and thus minimize the occurrence of missing data, including from those participants who may have been less successful in the intervention or follow-up period.**
  - **To allow for payments that are both convenient and rapidly available, we may pay participants with reloadable prepaid cards through Greenphire ClinCard ([www.greenphire.com](http://www.greenphire.com)), an FDIC-insured payment provider that specializes in clinical trial stipend payments that comply with IRB privacy regulations and considerations. At the beginning of the study, the participant will receive a prepaid MasterCard debit card that can be used anywhere that accepts MasterCard. As payments are earned in the course of the study, additional funds will be added to the account for that participant. Funds are immediately available when added and participants can check their balance as desired. This system will allow frequent, immediately available payments. Payments may also be made via check or cash, however remote debit card payments and checks will be used most often.**
  - **Compensation will be prorated.**
  - **To minimize barriers to participation, participants may also be provided with travel compensation in addition to the amounts above if they live outside of Roanoke or if travel to FBRI from within Roanoke is prohibitive to participation. Travel compensation, if provided, will be calculated using an hourly rate equal to the US minimum wage.**

32. Will you, the sponsor, or Contract Research Organization offer any fee to physicians for the referral of potential subjects?

Yes  No

33. Will recruitment materials be used?

Yes  No

If yes, check all that apply and include with this submission:

|   |  |
|---|--|
|  Brochure                       |  Radio/Television script   |
|  E-mail                         |  Newspaper Ad  |
|  Recruitment letter  |  Website advertisement (including Facebook, Craigslist, etc.) |
|  Flyer/Poster        |  Telephone or in-person script   |
|  Clinical trial website posting |  Other (please specify): Roanoke Valley Metro bus      |

### **STEP 1: IDENTIFICATION OF POTENTIAL SUBJECTS**

To "identify" a potential subject refers to steps you plan to take to determine which individuals may qualify to participate in your study so that you can decide which individuals to contact about taking part.

34. How do you plan to identify potential subjects? (check all that apply)

Medical Chart Review, Clinic Schedule Review, or QA-QI Database Review (own patient population)  
*\*Study team requests Waiver of Informed Consent and, if any HIPAA identifiers are collected, a Waiver of HIPAA Authorization for recruitment purposes*

Medical Chart Review, Clinic Schedule Review, or QA-QI Database Review (other physicians/practices patient population)  
*\*Study team requests Waiver of Informed Consent/HIPAA Authorization for recruitment purposes*

Potential subjects will not be directly identified by the researchers. The potential subject will obtain IRB-approved written information about the study from his or her health care provider/faculty or from an advertisement, flyer, brochure, website, etc. The potential subject would then contact the researcher if he or she is interested.

Researchers who ARE NOT treating clinicians of potential subjects will ask treating clinicians for referrals of eligible patients interested in the study. Treating clinicians identify potentially eligible patients and provide researchers with patient contact information with patient permission documented (e.g. email/letter to researcher from treating clinician states patient permission given. Researcher documents permission in research record.)  
*\*Study team requests Waiver of Informed Consent/HIPAA Authorization for recruitment purposes*

Contact information will be provided by a patient's Carilion health care provider without the patient's knowledge to the researchers AND this is a minimal risk study that does not involve investigative drugs, devices, biologics or medical or surgical procedures.  
*\*Study team requests Waiver of Informed Consent /HIPAA Authorization for recruitment purposes*

Review of Registry/Database in which individuals have previously signed a consent giving their permission to be contacted for future studies

Student Records  
*\*Study team requests Waiver of Informed Consent for recruitment purposes*

Other – please explain:

35. Please describe the identification process. List all information you plan to collect during the identification process prior to contacting potential subjects. This includes the inclusion/exclusion criteria and demographics to determine if a person qualifies for a study before contacting that person to be a potential subject.

Carilion Clinic personnel will conduct a data pull of potentially eligible patients from participating Carilion Family and Community Medicine clinics in the greater Roanoke Metropolitan area. An additional data pull may also include the New River Valley area. Data pulls will use the inclusion criteria of age  $\geq$  18, and may include BMI, HbA1c, prescribed glucose-lowering medications, as well as ICD-10 code for type 2 diabetes. The corresponding ICD-9 codes may also be used due to the transition from ICD-9 to ICD-10. Carilion Family and Community Medicine physicians will have an opportunity to review a list of their patients who have been identified as potentially eligible for this study at each data pull. These physicians will be able to request removal of any patient from the recruitment process. The data pull will use the exclusion criteria of no telephone number and patient stipulation of "Do Not Contact" as indicated in the medical record. The data pull will result in a list of potentially eligible patients, which will be provided to the PI. Identifying information in the data pull will consist of potentially eligible patients' names, addresses, and phone numbers. {

36. Who will conduct the identification process?

- Principal investigator
- Other investigator (specify):
- Research coordinator (specify): .
- Other research team member (specify): **Health Analytics**

